Problem: While cardiometabolic diseases such as coronary artery disease, atherosclerosis, hypertension, and type 2 diabetes, usually do not produce significant mortality and morbidity until adulthood, there is clear evidence that these diseases have their origins in childhood and adolescence. Studies of soldiers killed in Korea at average age of 22 years showed 77 percent had significant atherosclerosis.¹⁴ Autopsy studies of 15-34 years who died from accidental or non-accidental trauma demonstrated raised coronary artery lesions in individuals as young as 15 years with significantly increasing prevalence over time.¹⁵ In addition, with the rising incidence of obesity associated with poorer eating and less physical activity in children and adolescents it is important that we study these diseases early in their course if we are to prevent future cardiometabolic morbidity and mortality. A variety of techniques have been developed to assess early cardiovascular risk in this age group.¹⁶

The primary goals of this study are to explore the roles of complement components C3 and C4, physiology and genetics in relationship to cardiometabolic risk in Caucasian and African-American adolescents. Extensive literature exists (discussed below) indicating complement plays an important role in the development of future cardiometabolic disease.

Adipose tissue, endothelium and complement: Adipose tissue over the last 20 years has been demonstrated to produce and respond to a wide variety of hormones and inflammatory markers. For the purposes of this proposal the key factor is adipose tissue production and response to complement. Complement, a key part of the immune system, plays a central role in defense against micro-organisms. Chronic complement activation, however, may play a detrimental role in the development of cardiometabolic disease.¹⁷ Serum complement component C3 is vital to the three complement activation pathways and increased inflammation. C3 is manufactured by adipose tissue in adipocytes, macrophages and endothelial cells¹¹ and chylomicrons with dietary fat activate C3 production.^{18,19} The increased C3 is activated to the anaphyltoxins, C3a and C3b, through the alternative pathway and C3 concentration dependent tick-over rather than through increased inflammation since the ratios of C3a/C3 are not altered in obesity.^{18,20} C3a is rapidly cleaved by carboxypeptidases to remove carboxyl terminal of arginine to generate C3a-desArg.¹⁹

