Besides producing complement adipose tissue also responds to complement. Adipocytes have C3a (C3aR) and C5 receptors (C5aR1 and C5aR2). The C5aR2 is also the only known receptor for C3a-desArg.¹⁸ C3a-desArg, also known as acylation stimulation protein, plays an important role in lipid storage and energy metabolism. It accelerates adipocyte triglyceride metabolism and increases plasma triglyceride levels. This likely plays a role increasing insulin resistance.¹⁸ C3 and C3aR knock-out mice are resistant to diet-induced obesity and more insulin sensitive than control mice.¹⁸

Endothelial cells have anaphyltoxin receptors for C3a, C5a and other complement components that increase expression of cellular adhesion molecules and pro-inflammatory cytokines. C5a and C5b-9 are associated with increased endothelial dysfunction and e-selectin secretion.¹¹ The complement system is thought play a dual role in the development of atherosclerosis through removal of cellular debris and amplifying inflammation.¹¹ A wide variety of genetic complement modifications in mice have significant effects on atherosclerosis.²¹

Complement and cardiovascular risk in humans: Cross-sectional and longitudinal studies in adults have shown consistent relationships between complement (C3, C3a, C3a-desArg and C4) and a variety of cardiometabolic diseases and risk factors. Specifically C3, C3a and C3a-desArg levels positively correlate with measures of obesity and visceral obesity in most ethnic groups and both sexes.^{17,20,22-27} Beyond this several studies have demonstrated increased C3 levels in adults with the metabolic syndrome independent of obesity^{20,25,27-30} and several studies have shown direct relationships with individual components of the metabolic

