Racial differences in cardiometabolic risk and complement: Multiple differences have been demonstrated between African Americans and Caucasians in the underlying pathophysiologic features of the metabolic syndrome. First and foremost, African-American adults and adolescents have consistently been shown to have lower triglyceride levels and higher HDL levels than Caucasians.^{8,10,58} Beyond this, African-American adults have impaired endothelial function compared to Caucasian adults. Specifically, endothelin 1, a potent vasoconstrictor, is increased in African Americans adults⁵⁹ and flow mediated brachial artery vasodilation⁶⁰ is diminished. Hinderliter et al^{61,62} found higher minimum FVR following vascular occlusion in African American, young adults compared to similar aged, Caucasian subjects. Endothelial dysfunction is an early predictor of both cardiovascular disease and type 2

diabetes⁶³. African-American adults, also, have increased carotid artery intima-medial thickness⁶⁴. Adolescent African-Americans with a family history of essential hypertension have increased basal and stress-stimulated endothelin 1 levels compared to similarly-selected, Caucasian adolescents⁶⁵.

In adolescents, [name] has demonstrated decreased endothelial function and increased insulin secretion in African-American adolescents⁶⁶. The endothelial dysfunction occurred primarily in the obese adolescents with diminished post-occlusion shear stress-induced vasodilation⁶⁷. In a follow up study obese African-American adolescents were found to have increased free fatty acid levels pre and post high fat meal compared to Caucasians despite having decreased triglyceride levels¹³. As discussed above there are significant interactions between complement and fat metabolism that could account for these differences.

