Insulin sensitivity and secretion: Subjects will be given 1.75 grams/kg of oral glucose (up to a maximum of 75 grams). Blood samples for measurement of plasma glucose and insulin levels will be drawn every 30 minutes for 120 minutes. Insulin sensitivity (IS) will be calculated using the Matsuda Index (IS = $10,000/\sqrt{[\text{fasting glucose} \times \text{fasting insulin}] \times [\text{mean glucose} \times \text{mean insulin}]}$)⁸¹ while insulin secretion (SEC) will be calculated as the change in insulin divided by the change in glucose from 0 to 30 min (SEC = $\Delta I_{0-30}/\Delta G_{0-30}$).⁸² DI will be calculated by multiplying both these values (DI = IS x SEC).⁸² Disposition index is an important predictor of future type 2 diabetes.⁸³

Subject Incentives: Subjects will be compensated \$100 for participation in the Study Visit.

Laboratory: Genomic DNA will be prepared from peripheral blood mononuclear cells and used for assessment of C3 genetic polymorphisms, gene copy-number variations of total C4, C4A, C4B, long genes and short genes. Cell bound levels of processed activation products C4d and C3d deposited on red blood cells will be determined by flow cytometry. B-lymphoblastoid cell lines for each subject enrolled in this study will be created to facilitate future molecular biologic and genetic studies.

Complement phenotypes: Protein levels for complement C3 and C4 from EDTA-plasma will be determined by single radial immunodiffusion (RID) assays using commercial kits from the Binding Sites (UK). Fast and Slow protein variants of complement C3, acidic C4A and basic C4B allotypes of complement C4 will be elucidated by immunofixation of EDTA-plasma resolved by high voltage agarose gel electrophoresis, and scanned by densitometer to quantify the relative expression levels of polymorphic variants.⁷⁴ C3a-desArg will be assayed by enzyme-linked immunosorbent assays (ELSA) using EDTA-plasma and commercial kits (BD Bioscience). Cell-bound levels of processed complement activation products on erythrocytes, E-3d and E-C4d, will be assayed by flow cytometry using specific monoclonal antibodies against C3d and C4d, respectively (Quidel).⁸⁴

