Complement genotypes: C3 genetic variants including the DNA sequence polymorphisms for G102R for fast and slow allotypes, and SNPs for rs11569562 and rs2250656 that modulate C3 plasma protein levels will be typed for all study subjects. Copy-number variations for total C4, C4A, C4B, long genes and short genes of C4 will be elucidated by Southern blot analyses of genomic DNA samples digested by Pmel, Taql, PshAI/Pvull and resolved by gel electrophoresis.⁷⁴ Samples for subjects with ambiguous data will be subject to realtime quantitative PCR using five different amplicons and the results will be validated as the gene copy-numbers in each subject for total C4=C4A+C4B=long genes+short genes.⁸⁵

Cardiovascular measures, glucose and insulin: IL6, CRP, endothelin 1, fibrinogen, PAI1 glucose and insulin will be measured in the CORE laboratory. Plasma lipids will be measured in the clinical laboratory of the Wexner Medical Center.

Data analysis: **Specific Aim 1:** To determine whether there are racial differences in complement C3 and C4 levels in healthy adolescents and how they relate to cardiometabolic risk factors including triglyceride and LDL levels, inflammation, and vascular function.

Statistical methods: Complement levels from African-Americans in this proposal will be compared to those from nonHispanic whites in our current study. Eligibility criteria are identical for both studies except for race. Data will be assessed for normality using the Shapiro Wilk test ($p>0.05$ indicative of normality). Non-normal data will be log normalized if possible. Unpaired t-tests will be used to compare differences in C3 and C4 levels as well as cardiometabolic risk factor results (reactive hyperemia, augmentation index, Matsuda index, insulin secretion, lipids, inflammatory markers, and PAI-1). We anticipate age and BMI differences will be minimal but should racial differences be found analysis of covariance will be done to account for any difference found.

Robust rank order regression analysis will be used to assess relationships between C3 and C4 protein levels to body habitus, lipids, inflammation, carbohydrate metabolism, and clotting factor in each race individually and in the group as a whole. Age and sex will be included in all models. The cut-off point for outliers was 3 and 100 iterations were performed. Results are presented as 95% confidence intervals.

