Sample size: Based on data from our previous study with 100 nonHispanic white subjects and 100 African-American subjects we have power 0.8 to detect a 15% racial difference in C4 levels and 7.5% difference in C3 levels.

Interpretation: There are two major portions of this aim. The first is to determine whether there are complement levels differences between the racial groups and the second is to determine how these affect previously demonstrated racial differences in cardiovascular risk¹². The former will be easily determined by comparing complement levels in the two groups. The hypothesis that these racial differences are responsible for at least some of the cardiometabolic racial differences will be proven if when complement levels are included in the regression equation they retain significance but the racial differences are lost. Lastly, even if racial differences in complement are not found or do not account for cardiometabolic risk differences it will still be important for us to determine whether the significant effects of complement described above in nonHispanic whites are present in African-American adolescents.

Specific Aim 2: To determine whether specific C3 polymorphisms, F versus S, A>G at rs11569562 and/or rs2250656, are associated with increased cardiometabolic risk in African-Americans.

Statistical Methods: As indicated above, the C3F gene has been associated with increased risk of myocardial infarction in several populations³⁶⁻³⁸ and Phillips et al⁴⁰ reported increased cardiometabolic risk in subjects with either an A/A or A/G versus subjects with a G/G genotype for both the rs11569562 and the rs2250656 sites. For rs11569562 in a European population ~ 25% of subjects had G/G and for rs2250656 ~10% had G/G. Frequencies in the African-American population are unknown. Data will be assessed for normality using the Shapiro Wilk test ($p>0.05$ indicative of normality). Non normal data will be log normalized if possible. Unpaired t-tests with unequal sample sizes will be used for comparisons for each of the measured normal variables between subjects with at least one A allele gene and those with two G alleles assuming the data is normally distributed. Mann-Whitney U tests will be used to assess non-normal data.

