Limitations: This study is limited to studying C3 and C4 genetic differences and their relationships to differences in complement and cardiometabolic risk factors and not social and lifestyle differences between the two racial groups. An extremely interesting finding would be racial differences in complement levels without significant difference in complement genetics. This would suggest that differences in lifestyle (physical activity, socioeconomic stress) may play a significant role in causing complement racial differences. Even if no racial differences are found, these studies will still generate important information regarding the relationship of complement to cardiometabolic risk in adolescents and will indicate what areas should be explored to gain a better understanding of the racial risk differences.

Future Directions: Correlational, cross-sectional studies do not prove causation so if these results demonstrate significant relationships between complement and/or complement genetics in cardiometabolic risk then future longitudinal follow-up studies will be important. It would also be important to extend these findings to additional ethnic groups. Examining the effects of socioeconomic and cultural differences on the relationships of complement to cardiometabolic risk factors may also be of value. Our results also have potential value to inform future treatment studies to prevent or reduce cardiometabolic risk. The most immediate would be using complement genetics to potentially identify subjects at high risk for future cardiometabolic disease. Furthermore, various anti-complement therapies are being developed for use in a variety of diseases.⁸⁶⁻⁸⁸

REFERENCES

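### Aim 1 treats a pattern of significance in a cross-sectional regression as proof that complement causes racial risk differences; Future Directions says such data cannot prove this, and the rule can also be met when lipids drive C3

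*Combined protocol and SAP*

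**What the plan says.** The Interpretation paragraph under Data analysis, Specific Aim 1, divides the aim in two: whether complement levels differ by race, and how such differences bear on racial differences in cardiovascular risk. For the second part it sets a decision rule. The hypothesis that complement differences are "responsible for at least some of the cardiometabolic racial differences will be proven" if, once complement enters the regression, "they retain significance but the racial differences are lost". The outcomes include lipids: the aim asks "how they relate to cardiometabolic risk factors including triglyceride and LDL levels, inflammation, and vascular function".

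Future Directions states that "Correlational, cross-sectional studies do not prove causation" and leaves the causal question to later longitudinal work. The Protocol section describes one Study Visit.

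Background and Significance (Adipose tissue, endothelium and complement) describes both directions between lipids and C3. In one, "chylomicrons with dietary fat activate C3 production". In the other, of the C3 product C3a-desArg: "It accelerates adipocyte triglyceride metabolism and increases plasma triglyceride levels".

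The Aim 1 Statistical methods name age and sex as covariates in all regressions. They add analysis of covariance if age or BMI differs by race. They do not write out the regression with a race term that the rule needs.

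**The concern.** The rule turns a change in statistical significance into a causal finding. In one visit, complement and the risk factor are measured together, so the regression cannot show which came first or whether a third factor drives both. The protocol says as much in Future Directions, but that statement does not amend the rule, so a result could be declared proven under one section that another section says cannot be.

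The problem is concrete for lipid outcomes. The Background reports that "African-American adults and adolescents have consistently been shown to have lower triglyceride levels", and that C3 is lower in African-American adults. Lower lipids leading to lower C3 would give that pattern, and so would lower C3 leading to lower lipids. Nothing in the Aim 1 methods separates the two. The Specific Aims section looks ahead to targeted therapeutics, for which direction is what matters.

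**Working it through.** **1. The plan's own figure.** The rule has no operating characteristics attached. The only Aim 1 figure is power 0.8 with 100 + 100 subjects for differences of 15% (C4) and 7.5% (C3). No SD is given, so it can only be back-solved (two-sided alpha 0.05 assumed): detectable d = (1.96 + 0.84) × √(2/100) = 0.396 SD, implying a CV of 0.15/0.396 = 37.9% for C4 and 0.075/0.396 = 18.9% for C3. Nothing below depends on it.

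**2. Inputs for the direction check.**
- Group sizes: 100 African-American subjects, with 100 white subjects (Aim 1 Sample size) or 75 (Preliminary Studies).
- Unadjusted C3–triglyceride slope, Table 1: 0.054 (0.025 to 0.083), n = 75. With 71 df, SE = (0.083 − 0.025)/(2 × 1.994) = 0.01454, t = 3.71, partial r = 3.71/√(3.71² + 71) = 0.40.
- Waist-adjusted slope, Table 1: 0.009 (−0.027 to 0.046). SE = 0.073/(2 × 1.994) = 0.0183, t = 0.49, r = 0.49/√(0.49² + 71) = 0.06.
- Race difference in triglycerides: no size is given. **Assumed** 0.35 to 0.5 SD.
- Within-race r: 0.4 from Table 1. The upper value 0.6 is **assumed**.

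**3. Reverse model.** Let G be race, TG = −d·G + e and C3 = r·TG + √(1 − r²)·u, with e and u standard normal. C3 has no effect on TG. Regressing TG on G and C3 gives a C3 slope of r and a race coefficient of −d(1 − r²). At d = 0.4, r = 0.4 that is −0.4 × 0.84 = −0.336 (simulated −0.338). At r = 0.6 it is −0.4 × 0.64 = −0.256 (simulated −0.258). The race term shrinks by r² but does not vanish.

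**4. How often the rule is met.** The rule was coded as: race p < 0.05 alone; then C3 p < 0.05 and race p ≥ 0.05 together. There were 3,000 studies per setting.

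| Setting | Rule met |
|---|---|
| d 0.35–0.5, r 0.4–0.6, among studies with a significant race difference | about 6–34% |
| of which d = 0.35, r = 0.4 | 16–18% (10–11% of all studies) |
| same grid, C3 also required to differ by race (p < 0.05) | about 2.5–20% |
| of which d = 0.35, r = 0.4 | about 7% (about 4% of all studies) |
| r = 0.06 (waist-adjusted) | under 0.5% of all studies |

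Entries move by a point or two between runs. These are ordinary regressions; the plan specifies a robust rank method. A spot check on ranks at d = 0.4, with 100 per group, gave 11.7% against 12.3% (r = 0.4) and 28.5% against 26.3% (r = 0.6).

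At r = 0.4 the race coefficient shrinks by only 0.4² = 16%. The rule can fire because a modest shrinkage moves a borderline p-value across 0.05.

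**5. Reverse model with a separate race-to-C3 path.** Full mediation through C3 has C3 = −D·G + e and TG = r·C3 + √(1 − r²)·u. Set d = rD in the reverse model and add a direct race effect on C3 of −D(1 − r²). Group means and within-race covariance then coincide, so the joint distributions are identical. For D = 0.8, r = 0.4: d = 0.32 and direct effect −0.672. Share of all simulated studies meeting the rule:

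| D, r | C3 → TG | TG → C3 |
|---|---|---|
| 0.8, 0.4 | 0.594 | 0.592 |
| 0.6, 0.6 | 0.688 | 0.696 |
| 1.0, 0.4 | 0.772 | 0.772 |

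No regression on these two variables and race can tell the directions apart in this case.

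**The case against.** The authors know the limit. Future Directions states it plainly, and the protocol uses proven loosely: the Interpretation paragraphs for Aims 2 and 3 apply it to purely associational results. The sentence after the Aim 1 rule speaks of complement accounting for risk differences, which is close to acceptable wording. This stands as an explanation of the language. It does not repair the rule, because responsible is a causal word and the criterion is the stated test for one of the two portions of Aim 1.

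The percentages are also open to challenge, and much of that challenge stands. The Aim 1 text can be read as requiring C3 to differ by race first, which lowers the range to about 2.5–20%. The top of the range needs r = 0.6, which the protocol does not supply. With the waist-adjusted slope the route almost disappears. The unadjusted slope is still a fair scenario, since the regressions list only age and sex, with analysis of covariance if age or BMI differs by race.

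A reader might infer three stronger things that the documents do not support:
- *That the rule is met whenever lipids drive C3.* It can be met. In the simplest reverse model this happens in a minority of studies.
- *That the protocol says fasting triglycerides drive C3.* The statement concerns chylomicrons and dietary fat, while sampling here follows an overnight fast, and the same section also describes the opposite direction.
- *That the reverse route covers every Aim 1 outcome.* It concerns lipids, not vascular function or inflammation.

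**Conclusion.** The concern holds in this form. The Aim 1 rule and Future Directions contradict each other on whether this single-visit design can prove that complement is responsible for racial risk differences. That rests on the text alone and applies to every Aim 1 outcome.

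For lipid outcomes there is a demonstrated way for the rule to give a wrong answer. With lipids driving C3 and no effect of C3 on lipids, it is met in about 6–34% of studies with a significant race difference, or about 2.5–20% if C3 must also differ by race. Both ranges assume a race difference of 0.35 to 0.5 SD and r of 0.4 to 0.6. At r near 0.06 the figure is under 0.5% of all simulated studies. These figures show that the rule can mislead. They are not an estimate of this study's error rate.

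**What to change.** In the Aim 1 Interpretation, replace the claim of responsibility and proof with a statement that complement statistically accounts for part of the race difference, and that direction and causation are not established. This agrees with Future Directions.

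Replace the criterion of significance kept or lost with three estimates per outcome, each with a 95% confidence interval: the unadjusted race difference, the complement-adjusted race difference, and the change between them. Write out the model with its race term. Use the same subjects and other covariates in both fits, so that the change reflects complement alone. The interval for the change must allow for the two estimates coming from the same data, for example by bootstrap.

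Do not add a reversed regression (C3 on race and the lipid) to decide direction. As step 5 of the working shows, the two directions can give identical data. A rule that withholds a causal claim only when both models fit would imply that one is allowed otherwise.

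The cost is a change of wording and some extra reporting, with no new data or visits. The downside is a weaker headline claim.

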Regarding complement, African-Americans have been shown to have increased C4 levels⁶⁸, differences in C4 gene copy number in relationship to lupus⁶⁹⁻⁷², and different C3 polymorphism frequencies⁷³ than Caucasians. Regarding the latter have higher C3s allele frequency compared to Caucasians (93 versus 83%).⁷³ [name] studied the relationships between complement and obesity in 189 African American (Black) and 331 Caucasian (White) adult subjects from central Ohio.^{74,75} Between race differences in C3 and C4 levels were noted with increased BMI and C4 levels and decreased C3 levels in African-Americans. In each race group, strong correlations were seen between C3 and C4 protein concentrations, C4 protein levels and gene copy number of C4, BMI and C3 concentrations, BMI and C4 concentrations, and BMI and yield of C4 protein per copy of gene. In an earlier study of Hungarian subjects, positive correlations between serum C3 levels and total cholesterol concentration and between C3 levels and triglyceride levels were seen.⁴⁴

Significance: There are three important areas of innovation in the proposed studies.

1. ***Our study will be the first to explore the relationships of C3 and C4 levels to cardiovascular risk factors in African-Americans.*** This is important follow-up to our current study of nonHispanic Caucasian adolescents (Data presented below) because of the demonstrated differences in cardiovascular disease between African-American and Caucasian adults and in cardiovascular risk in adolescents. These studies will help us determine potential mechanisms for these differences early in the course of the disease.
2. ***Our study will be the first to explore the relationship between C3 polymorphisms and traditional and non-traditional anthropometric, biochemical, and functional cardiometabolic risk factors in African American adolescents.*** No studies have been done examining the role of C3 polymorphisms on cardiometabolic risk in adult or adolescent African-Americans. Again because of the increased cardiovascular disease and risk and because of the different polymorphism frequency in African-Americans it is clearly important that this population be studied.

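### Aim 1 claims a partial complement contribution to racial risk differences, but its only stated criterion needs the race effect to lose significance

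*Combined protocol and SAP*

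**What the plan says.** All references are to the combined protocol and SAP.

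- **Specific Aim 1, Interpretation.** The second portion of the aim asks "how these affect previously demonstrated racial differences in cardiovascular risk". The hypothesis is partial: "The hypothesis that these racial differences are responsible for at least some of the cardiometabolic racial differences". It "will be proven if when complement levels are included in the regression equation they retain significance but the racial differences are lost". The next sentence foresees only that complement differences are absent or do not account for the risk differences. A race effect that shrinks but stays significant is not mentioned.
- **Specific Aim 1, Statistical methods.** Complement and risk factors are compared between races by t-test. For age and BMI, "should racial differences be found analysis of covariance will be done to account for any difference found". Rank regressions relate complement to risk factors "in each race individually and in the group as a whole. Age and sex will be included in all models". No estimate of the change in the race effect is named, and the plan does not say whether C3 and C4 enter together or separately.
- **Specific Aim 1, Sample size.** "we have power 0.8 to detect a 15% racial difference in C4 levels and 7.5% difference in C3 levels". Nothing is sized for the second portion of the aim.
- **Background, racial differences.** In adults the text reports "increased BMI and C4 levels and decreased C3 levels in African-Americans", and within each race "strong correlations were seen between C3 and C4 protein concentrations".
- **Future Directions.** The plan accepts that cross-sectional correlations cannot establish causation.

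**The concern.** If complement explains part of a racial gap, the rest of the gap remains once complement is in the model. A criterion that needs the race term to become non-significant therefore tends to fail in the case the hypothesis describes. It also depends on sample size in the wrong direction: more subjects make a remaining race effect easier to detect, so a true partial contribution is less likely to be recognised.

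This is the only stated criterion for half of Aim 1. The likely loss is that a real partial contribution goes unrecognised although the same data could show it.

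C3 and C4 may also pull in opposite directions. The Background reports lower C3 and higher C4 in African-American adults, and worse endothelial function in African-American adolescents. The preliminary data show reactive hyperemia worsening as either protein rises. For that outcome C4 would shrink the race gap and C3 would widen it, so a single joint model can hide both paths.

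**Working it through.** **1. The plan's own figure.** With 100 per race, two-sided 0.05 (assumed; Aim 1 states no alpha) and power 0.8, the detectable difference is (1.96 + 0.84) × √(2/100) = 0.396 SD (0.398 with the t distribution). The stated 15% and 7.5% then imply coefficients of variation of 15/0.396 = 37.9% for C4 and 7.5/0.396 = 18.9% for C3. The plan gives neither, so its figure is coherent but cannot be verified. I use 0.40 SD as the complement gap; it is the detectable gap, not an expected one.

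**2. Slopes, from Table 1 (75 white adolescents, not adjusted for adiposity).** t = β / (CI width / 3.99); partial r = t / √(t² + 71).

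| Pair | t | partial r |
|---|---|---|
| C3, triglycerides | 0.054/(0.058/3.99) = 3.71 | 0.40 |
| C4, reactive hyperemia | 0.028/(0.030/3.99) = 3.72 | 0.40 |
| C3, HDL | −0.012/(0.022/3.99) = −2.18 | −0.25 |

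These are pairs for which the racial directions in the Background and the slopes in Table 1 agree. After the plan's body-habitus adjustment, C3-triglycerides falls to 0.06 and C3-HDL to 0.05. C4-reactive hyperemia stays at 0.32 and C3-reactive hyperemia at 0.25.

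**3. Model.** Complement = gap × race + noise. Outcome = direct × race + slope × complement + noise of variance 1 − slope². Direct = gap × slope × (1 − share)/share. The plan gives no mediated shares, so 25, 33 and 50% are assumptions. At slope 0.40 the indirect effect is 0.16 SD and the remaining race effect is 0.48, 0.32 or 0.16 SD.

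**4. Hand check.** In the joint model the standard error of race is about √0.84 × √1.04 × √(2/100) = 0.132. At 25% mediated, 0.48/0.132 = 3.6, so race is non-significant in only about 5% of trials. With 200 per race the standard error is 0.132/√2 = 0.093 and the ratio 5.1, so the criterion is almost never met.

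**5. Simulation** (least squares, age and sex in both models, 100 per race). Both methods require race to be significant on its own first. The direct test is a 95% CI for the indirect effect that excludes zero in the direction of the gap.

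| Slope | Share mediated | Initial race gap significant | Plan's criterion | Direct test |
|---|---|---|---|---|
| 0.40 | 25% | 99% | 5% | 81% |
| 0.40 | 33% | 92% | 25% | 76% |
| 0.40 | 50% | 61% | 39% | 54% |
| 0.25 | 25% | 80% | 23% | 62% |
| 0.25 | 33% | 55% | 26% | 44% |
| 0.25 | 50% | 29% | 18% | 24% |

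A rerun agreed within about two points. Ranking outcome and complement, one reading of the planned method, gives the same pattern.

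**6. Sample size.** At slope 0.40 and 25% mediated, with 50/100/200 per race, the criterion is met in 17/5/0.1% and the direct test succeeds in 50/81/98%. At 50% mediated, with 50/100/200/400 per race, the criterion is met in 22/39/50/33% against 24/54/88/99%. The reversal therefore comes later when less race effect remains.

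**7. C3 and C4 together.** With equal and opposite paths (gaps of −0.40 and +0.40 SD, slopes 0.40, assumed correlation 0.2 to 0.6, outcome gap 0.3 to 0.5 SD), the criterion is met in 1–7% of trials. The CI for the total change excludes zero in 3–5%, and the CI for C4's own indirect effect in 42–77%.

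**8. False proof.** With no complement gap, the criterion is met in about 4% of trials or fewer if either a race gap or a complement gap in this sample is required.

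**9. Adiposity.** I simulated no complement effect, C3-adiposity r = √0.41 = 0.64 (Preliminary Studies, FMI), assumed outcome-adiposity r 0.6, a racial adiposity gap of 0.3–0.4 SD, and a direct race effect of 0.1–0.3 SD in the same direction. The unadjusted direct test falsely declares support in about 20–43% of trials and the plan's criterion in about 6–22%. After adiposity adjustment both are about 0%.

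**The case against.** - **The condition is only sufficient.** This is correct. A reader might infer that the plan would reject the hypothesis whenever race stays significant; the text does not say so, and results with 95% CIs could still be discussed. But no other criterion is given, and the change in the race effect, which such a discussion would need, is not planned.
- **The result is built in.** Partly so: a rule that needs race to lose significance must fail when a large race effect remains. That is the mismatch with a partial hypothesis. When little race effect remains the rule does better. If no initial race gap is required, it is met in about 80% of trials at 50% mediated.
- **A model with race and complement is described.** The Interpretation text does imply one. It is under-specified, not absent.
- **The inputs are assumed.** This stands for the sizes, which rest on the detectable gap, invented shares and unadjusted slopes from white adolescents. The case of opposed C3 and C4 paths also relies on adult data. The logical mismatch does not depend on these values.
- **The rule manufactures proof.** A reader might infer this, because with neither gap required and no complement difference it is met in 67/36/14/3% of trials at race effects of 0.2/0.3/0.4/0.5 SD (slope 0.40). The documents do not support that reading. The hypothesis refers to existing complement differences, their absence is handled as a separate case, and a race difference cannot be lost unless there was one.
- **An unadjusted direct test could mislead more than the present rule.** This stands (step 9, where adiposity and outcome gaps run the same way) and shapes the fix.

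**Conclusion.** The concern holds in a limited form. The Aim 1 criterion does not match its partial hypothesis. When a sizeable race effect remains, it misses most true partial contributions, and a larger study misses more of them. At a 0.40 SD complement gap and slope 0.40, the shortfall against a direct test is 81 − 5 = 76 percentage points at 25% mediated and 54 − 39 = 15 points at 50%. At slope 0.25 it is 62 − 23 = 39 and 24 − 18 = 6 points, because the small initial race gap then limits both methods. These sizes are conditional on the assumptions listed; the mismatch is visible in the text alone.

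The documents do not support a claim that the plan invites frequent false proof through an absent complement gap. Nor do they support treating attenuation unadjusted for adiposity as evidence of a complement effect, since the plan's own data tie C3 closely to fat mass. The word *proven* goes further than Future Directions allows. The point should be fixed; it concerns interpretation in an exploratory study and does not affect the data collected.

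**What to change.** 1. For each outcome that differs by race in this sample, fit the pooled regression with race, age and sex, with and without complement, using the same method and covariates both times.
2. Enter C3 and C4 in separate models, then jointly, reporting each indirect effect separately.
3. Report the change in the race coefficient with a bootstrap 95% CI (resampling within race), both without and with adjustment for body habitus.
4. Read a result as consistent with a complement contribution beyond adiposity only if the adjusted CI excludes zero in the direction that shrinks the gap. If only the unadjusted CI does so, report it as possibly due to adiposity.
5. Report all outcomes and label the results exploratory: the Statistical methods list about ten (reactive hyperemia, augmentation index, Matsuda index, insulin secretion, three lipids, two inflammatory markers, PAI-1), each examined for both C3 and C4.
6. Replace *proven* with *consistent with*.

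**Cost.** No new data and a little more analysis. The answer becomes an estimate per outcome in place of a yes or no. Power after adiposity adjustment is low for most C3 outcomes: at slopes of 0.06–0.15, a 0.40 SD complement gap and an outcome gap of 0.4–0.5 SD, the CI excludes zero in 8–41% of trials. The present criterion would be met in 1–10% of the same trials.
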